## PROTOCOL SYNOPSIS

**Trial Title:** Gadopiclenol Pharmacokinetics, Safety and Efficacy in Pediatric Patients < 2 Years of Age Undergoing Contrast-enhanced MRI  
 Phase II Clinical Trial

Trial Product: G03277.100	Active Ingredient(s): gadopiclenol
EudraCT No.: 2021-003825-31	IND No.: 123673

Potential Participating countries (Potential Number of sites):

Worldwide trial involving approximately 15-20 centers in 4 regions/countries in Europe and USA.

### Trial Objectives

#### Primary objective:

To evaluate the pharmacokinetic profile of gadopiclenol in plasma following single intravenous injection of 0.05 mmol/kg body weight (BW) in pediatric population aged up to 23 months (inclusive) scheduled for a contrast-enhanced MRI examination of any body region including central nervous system (CNS).

#### Secondary objectives:

1. To evaluate the safety of gadopiclenol (clinical and biological) up to 3 months following single administration.
2. To evaluate the efficacy of gadopiclenol-enhanced MRI by body region (CNS, vessels and pool of others) as assessed by on-site Investigator.

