#### Secondary criteria:

- The following clinical and biological safety parameters/examinations will be measured/Performed:
  - Physical examination at visits 1, 2 (if applicable), 3, 4 and 5 including examination of general appearance, skin (including extremities), neck (including thyroid), eyes, abdomen, back, lymph nodes, peripheral vascular and neurological examination and other (any other observed abnormalities).
  - Vital signs (temperature, blood pressure, pulse rate and peripheral oxygen saturation ( $SpO_2$ )) at 3 time points: prior to IMP injection, 10-60 min and 1 day after IMP injection.
  - Safety laboratory variables centrally analyzed (biochemistry and hematology) from blood samples collected prior to and 1 day after IMP injection,
  - Estimated glomerular filtration rate (eGFR) centrally calculated based on the bedside Schwartz equation prior to and 1 day after IMP injection,
  - Tolerance at the injection site at 3 time points: during injection, 10-60 min and 1 day after IMP injection,
  - Adverse events (AE) occurring from the beginning of patient's participation in the trial (Informed Consent Form signature) until the end of the participation.
  - Clinical examination for active detection of Nephrogenic Systemic Fibrosis (NSF) at 3-month follow-up safety visit. In case of suspicion of NSF a deep skin biopsy will be performed.
- Efficacy will be assessed by the on-site radiologist for both pre-contrast (Pre) and pre+post contrast (Paired) images, assessments will be performed for the primary anatomical area to be evaluated based on following parameters:
  - Technical adequacy for diagnosis using a 4-point scale: non diagnostic (reasons to be provided), poor, fair and good.
  - Assessment of overall contrast quality using a 5-point scale: 1= None (for example, in case of a non-enhancing lesion), 2= Poor, 3= Moderate, 4= Good, 5= Excellent.
  - Number and location of lesions/abnormal vessels, the largest diameter (lesions only) of three most representative lesions/abnormal vessels will be recorded.
  - Quantitative assessment (not applicable for vessels): percentage of enhancement (E%) and Lesion to Background Ratio (LBR) and Contrast to Noise Ratio (CNR) for CNS only for up to 3 most representative lesions (largest enhancing lesions).

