 Any medication, including homeopathic products, over-the-counter medications, as well as prescription drugs, on-going at V1 or administered until V4 will be recorded in the patient's eCRF. Between V4 and V5 safety visits, newly started concomitant medications/treatments in patients experienced at least one AE will be documented. Any GBCA injection will be documented in all patients.

 At screening, blood sample will be collected to analyse biochemistry and hematology in central lab including measurement of serum creatinine and eGFR calculation. If centrally calculated eGFR is not available at V2, serum creatinine and eGFR can be obtained locally to confirm patient's eligibility, fingerstick capillary blood sampling at the point of care is acceptable.

Note: In any case the overall trial-related blood loss (including potential capillary blood sampling at the point of care for locally calculated eGFR) will not exceed the limit of 0.9 mL/kg body weight corresponding to 1% of total blood volume at a single time point and 2.4 mL/kg body weight (3% of the total blood volume during a period of four weeks).

 Contrast-enhanced MRI duration will correspond to the usual practice at site depending on the indication.

 All Adverse Events occurring from the beginning of the patient's participation in the trial (Informed Consent Form signature) and until V4, must be reported and followed even if no IMP was administered.

[figure not shown]
Non-serious AE occurring before IMP administration and not related to the trial can be collected as medical history or AE according to Investigator's opinion. Non-serious AEs occurring after V4 must be reported if related to the drug or to the trial and followed until recovery or sequelae stabilization.

 Serious Adverse Events (SAE) and Adverse Event of Special Interest (AESI) occurring from the beginning of the patient's participation in the trial (ICF signature) and until V5 must be reported and followed until recovery or sequelae stabilization (see [9.1.2](#)).

 Three blood samples will be drawn per patient, one during each time window: W1, W2 and W3 at time points allocated by randomization via IWRS.

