### 7.2 Secondary Criteria

#### 7.2.1 *Clinical and biological safety*

- Physical examination at visits 1, 2 (if applicable), 3, 4 and 5 including examination of general appearance, skin (including extremities), neck (including thyroid), eyes, abdomen, back, lymph nodes, peripheral vascular and neurological examination and other (any other observed abnormalities).  
Any clinically significant abnormality or change will be recorded as AE or medical history if examination performed prior to IMP administration upon Investigator's judgement.
- Vital signs (temperature, systolic and diastolic blood pressure, pulse rate and peripheral oxygen saturation (SpO2)) at 3 time points: prior to IMP injection, 10-60 min and 1 day after IMP injection.

Body temperature will be measured on forehead by infrared thermometer.

Blood pressure and pulse rate will be measured after a rest for at least 5 minutes in supine position. Blood pressure will not be measured on the arm used for the injection.

Peripheral oxygen saturation (SpO2) will be measured by pulse oximetry using a transcutaneous non-invasive light emitter.

If significant change in vital signs occurs, vital signs should be measured more frequently as long as necessary to ensure that the change has been resolved and/or that the subject is stable. Any clinically significant abnormality or change will be recorded as AE or medical history if vital signs performed prior to IMP administration upon Investigator's judgement.

- Safety laboratory variables centrally analyzed (biochemistry and hematology) from blood samples collected at screening and 1 day after IMP injection.

 CONFIDENTIAL	Protocol No. GDX-44-015 Version No. 4.0 including amendments 1 & 2 & 3 Date 09 Oct 2023	F015919-05 Page 40 / 75
---	---	----------------------------

- Hematology: red blood cells (RBCs), white blood cells (WBCs) counts: neutrophils, eosinophils, basophils, lymphocytes and monocytes, platelet count, hemoglobin, hematocrit, mean red blood cells volume (MCV).
- Biochemistry: sodium, potassium, chloride, blood urea nitrogen (BUN), creatinine, total protein, calcium, phosphorus, iron, ferritin, transferrin, total bilirubin, conjugated bilirubin, aspartate amino transferase (AST), alanine amino transferase (ALT), alkaline phosphatase, lactate dehydrogenase (LDH), PT (prothrombin time) / INR (International Normalised Ratio).

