- Estimated glomerular filtration rate (eGFR) calculated by central lab based on the bedside Schwartz equation prior to and 1 day after IMP injection.

Bedside Schwartz equation [\[2222-24\]](#) will be used with creatinine methods with calibration traceable to isotope dilution mass spectroscopy (IDMS):

$$\text{eGFR (mL/min/1.73 m}^2\text{)} = (0.413 \times \text{Height in cm}) / \text{Standardized Serum creatinine (mg/dl)}$$

Post-contrast acute kidney injury (PC-AKI) is defined as an increase in sCr of  $\geq 0.3$  mg/dl or sCr  $\geq 1.5$  times baseline. Such changes will be monitored, and additional information may be requested to the Investigator.

Any clinically significant abnormal value or change will be recorded as AE. Any abnormal value on sampling performed prior to IMP administration could be recorded in medical history upon Investigator's judgement.

- Tolerance at the injection site (eruption, extravasation and inflammation) at 3 time points: during injection, 10-60 min and 1 day after IMP injection.
- Adverse events (AE) occurred from the beginning of patient's participation in the trial (Informed Consent Form signature) until the end of the participation.
- Clinical examination for active detection of Nephrogenic Systemic Fibrosis (NSF) at 3-month follow-up safety visit. In case of suspicion of NSF a deep skin biopsy will be performed.

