## 9 SAFETY REPORTING

The Investigator will report to Guerbet any adverse event whether related or not to the investigational medicinal product, serious or not, that occurred in a trial patient during its participation to the trial. Special situations such as treatment errors, misuses, suspicion of transmission of an infectious agent via an IMP, unusual failure in efficacy, overdose (symptomatic or not), suspected drug-drug interaction with another product (symptomatic or not) will also be reported to Guerbet.

The definition, modalities of collection and reporting are provided below.

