### 11.3.8 *Adverse Event*

An overall summary of AEs will be presented using the All enrolled set to catch AEs of patients who did not receive trial drug. The table will be presented overall and only with the following variables:

- Total number of AEs
- Total number of patients with at least one AE
- Distribution of the number of AEs reported by patients (0, 1, 2 or 3 or more AEs)
- Total number of Serious AEs (SAEs)
- Total number of patients with at least one SAE
- Total number of AEs according to intensity (severity)
- Total number of patients with at least one AE according to intensity (severity)
- Total number of AEs according to the outcome
- Total number of patients with at least one AE according to the outcome
- Total number of AEs requiring a concomitant drug (other action taken)/procedure-Total number of patients with at least one AE requiring a concomitant drug (other action taken)/procedure

 CONFIDENTIAL	Protocol No. GDX-44-015 Version No. 4.0 including amendments 1 & 2 & 3 Date 09 Oct 2023	F015919-05 Page 63 / 75
---	---	----------------------------

- Total number of AEs leading to the patient's withdrawal from the study Events will be classified as treatment-emergent (TEAE) if they started after drug administration.

The same overall summary will be displayed by age group for Treatment Emergent AEs (TEAEs) using the Safety Set. The following variables will be also presented:

- Total number of TEAEs with causal relationship to the trial IMP.
- Total number of patients with at least one TEAE with causal relationship to the trial IMP.
- Total number of TEAEs requiring withdrawal of trial IMP.
- Total number of patients with at least one TEAE requiring withdrawal of trial IMP.

The number and percentage of patients with at least one TEAE will be presented using the Safety Set by age group according to Primary SOC and PT.

The number and percentage of patients with at least one TEAE with causal relationship to the IMP will be presented using the Safety Set by age group according to Primary SOC and PT.

The number and percentage of patients with at least one SAE or AESI will be presented using the Safety Set by age group according to Primary SOC and PT.

The number and percentage of patients with at least one SAE or AESI with causal relationship to the IMP will be presented using the Safety Set by age group according to Primary SOC and PT.

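### Secondary objective 1 claims clinical and biological safety to 3 months, but scheduled laboratory and vital-sign data end at 1 day and the all-TEAE tables mix two collection rules

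*Protocol*

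**What the plan says.** **Objective.** The Protocol synopsis, Protocol 2.2 and SAP 7.1.2 all give the first secondary objective as "To evaluate the safety of gadopiclenol (clinical and biological) up to 3 months following single administration".

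**Laboratory tests, eGFR and vital signs.** The synopsis criteria list "Safety laboratory variables centrally analyzed (biochemistry and hematology) from blood samples collected prior to and 1 day after IMP injection". Section 7.2.1 says the same of the laboratory panel ("from blood samples collected at screening and 1 day after IMP injection") and has eGFR "calculated by central lab based on the bedside Schwartz equation prior to and 1 day after IMP injection". Vital signs have three time points, the last at 1 day. The visit lists for V4 (8.1.4) and V5 (8.1.5) contain neither a blood sample nor vital signs. Section 8.5.1 allows further measurements when the investigator wants to follow an abnormal value.

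**Adverse events.** Footnote 7 of the Trial Flow Chart ends general collection at V4 and adds: "Non-serious AEs occurring after V4 must be reported if related to the drug or to the trial". Table 2 (Section 9.1.2) agrees: unrelated non-serious AEs have no entry at V5, while unrelated SAEs, AESIs and related AEs do. Two other places read more broadly. Section 7.2.1 lists "Adverse events (AE) occurred from the beginning of patient's participation in the trial (Informed Consent Form signature) until the end of the participation", as the synopsis does in nearly the same words, and Section 9 opens with "The Investigator will report to Guerbet any adverse event whether related or not to the investigational medicinal product, serious or not", covering the time of participation.

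**Analysis.** Section 11.3.8 states: "Events will be classified as treatment-emergent (TEAE) if they started after drug administration". It tabulates TEAEs by age group, and by SOC and PT, with no division by period.

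**The concern.** The objective sets one horizon, 3 months, for two kinds of safety, while the schedule has three horizons: 1 day, V4 and V5. Two things follow if the report is written to the objective.

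First, a statement on biological safety to 3 months would rest on a single scheduled post-dose sample in children under 2 years. Section 1.3 itself describes renal clearance in term newborns as immature and changing rapidly, so readers are likely to look at this result closely.

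Second, the all-TEAE tables would look like 3-month results. They would in fact combine a week in which every AE is collected with about 12 weeks in which a non-serious event is generally collected only if it has been judged related. The trial is uncontrolled, so no comparator arm carries the same selection.

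**Working it through.** **1. Reproduce the plan's own figure.** Section 3.3.1 gives participation of 83 to 104 days. The flow chart puts V5 at V2 + 89 ± 7 days, V2 is Day 1, and screening is up to 7 days earlier.
- V5 as a study day: 1 + 89 − 7 = 83; 1 + 89 = 90; 1 + 89 + 7 = 97.
- Minimum, with screening on the day of injection: 83. Maximum: 97 + 7 = 104. Both match.

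**2. Coverage of the span from injection to V5.** The span is 89 days (82 to 96). V4 is at 7 ± 1 days, so 6 to 8.

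| Component | Days covered | Share of span | Days not covered |
|---|---|---|---|
| Scheduled laboratory tests, eGFR, vital signs | 1 | 1/89 = 1.1% (1/96 = 1.0% to 1/82 = 1.2%) | 88 (81 to 95) |
| Unrelated non-serious AEs | 7 (6 to 8) | 7/89 = 7.9% (6/96 = 6.3% to 8/82 = 9.8%) | 82 (74 to 90) |
| SAEs, AESI, related AEs | whole span | 100% | 0 |

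**3. Effect on the all-TEAE tables.** Let D be the TEAEs actually collected, R those among them related to the IMP, and U the unrelated non-serious events with onset after V4, which Table 2 does not collect.
- Reported related share: R / D.
- Share under uniform collection to V5: R / (D + U).
- Ratio of the two: (D + U) / D = 1 + U/D.

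The numerator is complete to V5 and the denominator is not. The reported share is therefore too high whenever R and U are both above zero. The documents give no AE rate for this population, so U/D cannot be given a value.

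For the proportion of patients with at least one TEAE, the reported count lies between the count to V4 and the full 3-month count. It estimates neither.

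**4. Tables that are not affected.** Section 11.3.8 also plans separate tables for IMP-related TEAEs, for SAEs or AESIs, and for related SAEs or AESIs. Table 2 collects these categories under one rule from injection to V5.

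**5. The AE texts side by side.** Footnotes 7 and 8, Section 8.1.5 and Table 2 agree on what is collected after V4. Section 9 is broader, but its introduction defers to the rules that follow it, and 9.1.2 directs recording by Table 2. The synopsis criteria and Section 7.2.1 carry no such pointer. Section 7.2.1 also lists a physical examination at visit 5 and has any clinically significant abnormality or change recorded as an AE. An unrelated, non-serious finding at V5 would be recordable under that sentence and not under Table 2. Section 8.1.5 describes the V5 examination as directed at NSF, which is narrower than the general examination in 7.2.1.

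**The case against.** The strongest reply is that the design does address 3-month safety where it matters most. SAEs, the AESI and related AEs are collected to V5, V5 includes an NSF examination and a record of any GBCA injection, Section 11.3.10.4 tabulates NSF at 3 months, and Section 3.3.1 says V5 is there to monitor NSF risk. The criteria state each component's timing openly. The trial is descriptive (11.1), and sparse sampling fits both its aim of limiting burden and its blood-loss limits. All of that stands, and it rules out four stronger readings that a reader might infer.

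- *The design cannot answer the objective.* This is not so for clinical safety, for the reasons just given.
- *There are no biological data after Day 2.* Section 8.5.1 allows unscheduled follow-up of abnormal values, and AEs are followed to recovery or stabilization. What is missing is a scheduled sample. Selective follow-up of abnormal values does not describe the cohort.
- *Every non-serious event recorded after V4 is related by construction.* Section 9.3.3 allows an AESI to be non-serious, and Table 2 collects AESIs to V5 whatever their causality.
- *Sites will report differently.* Section 9.1.2 points to Table 2, so the operative rule can be found. The broader texts call for a cross-reference and are not evidence of divergent reporting.

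A further reply is that Protocol Section 11 is only a summary of an SAP. The SAP supplied is the population PK analysis plan and contains no AE analysis. A separate safety plan might split TEAEs at V4, which cannot be checked from these documents. That limits the certainty of the tabulation point. It does not affect the objective, which has the same wording in both documents.

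**Conclusion.** The objective overstates what the design supports. Biological safety to 3 months cannot be described for the cohort, because no laboratory or eGFR assessment is scheduled in the last 88 of 89 days. Vital signs stop at the same point. Clinical safety to V5 is supported for SAEs, AESI/NSF and related AEs; all AEs are covered for about 7 of 89 days.

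The all-TEAE summary and the all-TEAE SOC/PT table combine two collection rules. They do not give a 3-month incidence, and they inflate the related share of all TEAEs by a factor of 1 + U/D, of unknown size.

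This assumes that the schedule is followed as written, that Table 2 is the operative collection rule, and that no separate safety analysis plan already divides TEAEs by period. The inflation also needs at least one related TEAE and at least one unrelated non-serious event after V4. The point is more than a preference about wording, because it changes what the report may conclude.

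**What to change.** 1. **Restate secondary objective 1** in the Protocol synopsis, Protocol 2.2 and SAP 7.1.2 by component and horizon: scheduled laboratory tests, eGFR and vital signs to 1 day; all AEs to V4; SAEs, AESI/NSF and related AEs to V5. Limit the report's conclusion on biological safety to 1 day.
2. **Split the all-TEAE tables in 11.3.8** into onset up to V4 and onset after V4, with a note that the second period contains only SAEs, AESIs and related events. Use each patient's own V4 date, and state the rule for a patient without a V4. The onset date and time are already recorded (9.1.3).
3. **Reconcile by cross-reference.** The AE items in the synopsis criteria and in 7.2.1, the sentence in 7.2.1 on recording examination findings, and the opening of Section 9 should each refer to Table 2. The scope of the V5 examination should read the same in 7.2.1 and 8.1.5.

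The cost is a narrower stated safety claim and one extra table split. No visit, blood sample or patient is added, so the blood-loss limits are not touched. Whether later sampling should be added is a clinical decision and is not proposed here.

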### Trial design and methodology

This Phase II open-label, uncontrolled, multicenter trial is designed to investigate the pharmacokinetic (PK) profile of gadopiclenol in plasma, in pediatric patients aged up to 23 months inclusive (term neonates or preterm infants after the neonatal period), using a population PK approach. This approach, which allows sparse blood sampling, is selected to minimize the clinical burden to children. Blood sampling will be recommended via indwelling catheters rather than by repeated venipunctures.

A total of 3 blood samples per patient will be taken post-injection for PK analysis, one within each window:

- 10-60 minutes,
- 2-4 hours,
- 6-8 hours.

Each time window contains 4 time points for blood collection. One of the time points within each time window will be randomly allocated to the patients by Interactive Web Response System (IWRS).

Three age groups are defined:

- Group 1: patients aged 3 to 23 months (inclusive)
- Group 2: patients aged 28 days to less than 3 months
- Group 3: patients aged from birth to 27 days (term newborns).

The inclusions started with the oldest patients in Group 1.

The decision to start the inclusions in Group 2 was taken by the Trial Safety Review Board (TSRB) based on safety assessment over one-day period after injection of the first 13 patients in Group 1.

According to the protocol amendment N°2, the aged-down staggered approach is discontinued to allow the inclusions in Group 3 (patients aged from birth to 27 days), simultaneously to inclusions in

Group 1 and Group 2. The decision to start the inclusions in Group 3 will be implemented (if required country per country) upon the approval by CA and IRBs of the present amendment.

The inclusions in the three age groups will be completed in parallel.

However, the TSRB will continue to meet and review safety data, as described in the TSRB Plan.

### **Number of patients**

50 patients will be included in the trial assuming that at least 45 patients will be evaluable for the primary criteria.

Patients will be distributed between the 3 age groups as following:

- Group 1: at least 20 patients
- Group 2: at least 12 patients
- Group 3: at least 5 patients

At least 25 patients (50%) will be scheduled to undergo contrast-enhanced MRI of CNS (CNS cohort)

